7.2 Sample Size

To determine feasibility in a single-arm pilot trial (up to N=35), estimate effect size, and finalize the intervention and study protocol to apply for an NIH grant to conduct a full-scale efficacy trial.

7.3 Early Stopping Rules

Study participation will be terminated at any time upon the participant's request.

7.4 Definition of Allowance in Design for Unevaluable/Ineligible Participants

Not applicable.

7.5 Analysis Plan

Aim 1: Feasibility and acceptability will be measured by rates of enrollment (>50%), participant retention (>70%), intervention attendance (>70% attending at least 1 of 2 sessions), and intervention satisfaction (>75% reporting average satisfaction greater than the CSQ's midpoint).

Aim 2: First, data will be analyzed with the intention-to-treat principle and assessed for statistical assumptions and patterns of missingness, implementing Multiple Imputation with maximum likelihood if appropriate. Sample size justification. We may over-accrue to ensure that a total of up to 45 BCS complete the study. This pilot study will provide a preliminary estimate of the rate of AET initiation within one month from baseline. With up to 30 participants, the width of the exact 95% confidence interval (CI) for the rate of AET initiation at one month will be at most 37.4% (i.e., +/- 18.7%). If at least 24% of participants initiate AET within one month, the study will rule out a post-intervention initiation rate of lower than 10% based on the lower limit of the exact 95% CI. We will conduct exploratory analyses to examine whether participants' baseline characteristics are associated with AET initiation at one month using Fisher's exact tests and unpaired t-tests. For secondary outcomes, we will conduct paired samples t-tests to assess intervention-related changes in satisfaction with communication with clinicians and treatment, Necessity-Concerns Framework, perceived support, self-efficacy for managing side effects, and QOL from baseline to one-month post-baseline. In addition, we will use linear mixed effects regression models to evaluate the change in secondary outcomes across all three assessment time points. We will interpret 95% Confidence Intervals and Cohen's d effect sizes ($D = [(Mean 1) - (Mean 2)] / \text{pooled Standard Deviation}$), with magnitudes of 0.3, 0.5, and 0.8 for small, medium, and large effects, respectively. We will conduct sensitivity analyses to examine whether changes in outcomes are differ among racial and ethnic groups.

Participants will be given the opportunity to receive a summary of study results at the completion of the study. If a request is made, the study staff will provide the participant with an abstract of the study at the end of data collection and analysis.

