5.0 Study Design and Methods

5.1 Design/Study Type

The present protocol proposes to examine the single-arm pilot trial to examine feasibility and acceptability of a patient-centered, evidence-based, culturally competent, tailored intervention to encourage breast cancer survivors who have not begun taking adjuvant endocrine therapy to initiate the medication, enriching for Black, Hispanic/Latina, and Asian American BCS. AET initiation will be measured by a self-report questionnaire. Participants will complete assessments at baseline (within 14 days of consent), 1-month, and 3-months post-baseline measuring beliefs about AET necessity, satisfaction with patient-physician communication, perceived social support and quality of life.

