5.2 Selection of Instruments

Instrument/Measure	Screening	Baseline (14-day window)	1-month follow-up (+/- 7 day)	3-month follow-up (+/- 7 day)
Chart Review	X			
Screening Questions (AET initiation)	X			
Demographics		X		
AET Initiation Question		X	X	X
Functional Assessment of Chronic Illness Therapy- Treatment Satisfaction-Patient Satisfaction (FACIT-TS-PS)		X	X	X
Beliefs about Medicines Questionnaire – Adjuvant Endocrine Therapy (BMQ-AET)		X	X	X
Multidimensional Scale of Perceived Social Support (MSPSS)		X	X	X
Functional Assessment of Cancer Therapy-Breast (FACT-B)		X	X	X
Hospital Anxiety and Depression Scale (HADS)		X	X	X
Self-Efficacy for Managing Symptoms Questionnaire (Self-Efficacy for Symptoms)		X	X	X
Measure of Current Status – Part A (MOCS)		X	X	X
Client Satisfaction Questionnaire (CSQ)			X	

Screening:

EHR Factors: The following information will be collected from participant EHR: MGH Main vs Affiliate site vs DFCI sites, demographic information, breast cancer stage, treatment (e.g., surgery, chemotherapy, radiation), AET type, approximate recommended AET start date, and medical or psychological co-morbidities.

AET Initiation questions: A question will be administered asking patients whether they have started taking their daily AET (yes vs. no). Patients who have not yet started AET will be considered eligible for study participation. Patients will also be asked how hesitant they are about starting their recommended hormonal therapy medication on a scale of 0-10.

Outcome Measures:

Demographics Questionnaire: Participants will self-report their age, gender, race/ethnicity, marital status, education level, and relationship status.

AET Initiation Question: This one item instrument will ask patients: At different times throughout your participation in this study, you may or may not be taking/have started taking your hormonal therapy. “At this time, are you currently taking your hormonal therapy (e.g., Tamoxifen, Anastrozole/Arimidex, Exemestane/Aromasin, Letrozole/Femara)?” Patients will self-report their initiation of endocrine therapy.

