The intervention and study materials will be translated into Spanish and delivered by nurse practitioner, [name], in either English or Spanish. An interpreter will be present either in person or remotely for the intervention for patients who speak Spanish only. Both sessions will take place within one month of the baseline assessment. The intervention will target known modifiable barriers to AET initiation, including support and communication with clinicians, perceived therapeutic efficacy of AET, and managing expectations of symptoms and side effects, but will be primarily driven by barriers identified by the patient. Therefore, the session will begin by probing and identifying the individual and culture-specific barriers to initiation in multiple domains. The interventionist and patient will then problem-solve barriers to initiation through motivational interviewing, cognitive-behavioral techniques, and medication education. The intervention is informed by the Health Belief Model (HBM), the Cognitive Model of Adjustment to Cancer, and Motivational Interviewing Techniques. First, the intervention will address perceived risk and medication efficacy in line with the HBM, which maintains that the health behavior (i.e., initiating AET) will be adopted if the patient perceives (a) risk for a condition, (b) that the medication will reduce risk, (c) that benefits outweigh costs, and (d) self-efficacy for taking medication. Second, driven by the Cognitive Model of Adjustment to Cancer, the intervention will include strategies for enhancing coping with side effects, reframing cognitive self-talk about AET efficacy, and identifying and enhancing social support. CBT is effective in helping patients manage concerns, fears, and actual cancer-related side effects. Finally, Motivational Interviewing techniques will help the patient explore and resolve ambivalence with attention to their readiness for change. Sessions will be audio-recorded and at least 10% will be reviewed for treatment fidelity. Intervention acceptability will be evaluated using the CSQ.

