7.6 Handling of Missing Data in the Analysis

The analyses for this study will focus on study completers to estimate the effect of the 2-session, patient centered intervention. The primary endpoint will be based on acceptability and feasibility aspects of the study. We will use the intention-to-treat principle for analyses with all participants. After we examine patterns of missingness, we will use maximum likelihood with multiple imputation to account for missing data.

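### The one-month AET initiation rate is counted from baseline but called post-intervention, and no start date is collected to separate starts before session 1 from later ones

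*Combined protocol and SAP*

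**What the plan says.** Section 7.5 (Aim 2) sets the time origin at baseline: the pilot is to give a "preliminary estimate of the rate of AET initiation within one month from baseline". Its precision statement then renames the quantity: "If at least 24% of participants initiate AET within one month, the study will rule out a post-intervention initiation rate of lower than 10" per cent, judged by the lower limit of the exact 95% interval.

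The intervention comes after that origin. Under section 5.3, sessions begin once baseline and enrollment are complete and are about two weeks apart, and "Both sessions will take place within one month of the baseline assessment". The same section aims to hold both sessions before the planned AET start date, case by case.

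The outcome is one self-reported item (section 5.2): "At this time, are you currently taking your hormonal therapy". It is asked at baseline, 1 month and 3 months, with a window of 7 days either side of each follow-up. No date of first dose is described. The chart review in section 5.2 is scheduled at screening only and collects the approximate recommended start date, not the actual one.

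On the analysis set, section 7.6 says "We will use the intention-to-treat principle for analyses with all participants", although it also says that analyses will focus on completers. Neither sentence sets aside starts that precede session 1.

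**The concern.** The counting window opens at baseline and the intervention does not, so the window contains a stretch in which no session has taken place. A woman who answers no at baseline, starts AET a few days later and then attends session 1 gives the same answers as a woman who starts after both sessions. Both count towards the rate that section 7.5 calls post-intervention.

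Some starts in that stretch are plausible. One of the two eligible groups in Table 1 has a recommended start date in the future, and some of these women may begin on schedule. For the other group, whose recommended start was at least 3 weeks earlier, an aim to hold sessions before the planned start offers little protection.

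Section 7.2 says that the pilot is to estimate an effect size and support an application for an efficacy trial. With no control arm, the order of session and start is the minimum needed to link the two. If dates are not collected during the study, the instruments described cannot supply them later.

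**Working it through.** **Inputs.** From section 7.5: n = 30, exact two-sided 95% interval, stated maximum width 37.4%, threshold 24% observed to exclude 10%. From section 5.3: sessions about 2 weeks apart, both within one month of baseline. Not in the documents: the number k of women who start after baseline but before session 1. It is an assumption below, shown for k = 0 to 3.

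**1. Reproduce the plan's figures.** The exact (Clopper-Pearson) limits for x of n are:

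- lower = Beta quantile (0.025; x, n − x + 1)
- upper = Beta quantile (0.975; x + 1, n − x)

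The interval is widest at x = 15: 31.3% to 68.7%, width 37.4%, as stated. For the threshold, 0.24 × 30 = 7.2, so at least 24% means 8 women.

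| Result | Rate | Lower limit | 10% excluded? |
|---|---|---|---|
| 8/30 | 26.7% | 12.28% | yes |
| 7/30 | 23.3% | 9.93% | no |

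The plan's arithmetic is correct. The issue is what is being counted.

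**2. Length of the exposed period.** If both sessions fall within about 30 days and are about 14 days apart, session 1 is at most about 30 − 14 = 16 days after baseline, roughly two weeks.

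**3. Effect of reclassifying starts before session 1.** There are two ways to treat such women: recode them as non-initiators (denominator stays 30) or remove them from numerator and denominator.

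| Observed | Recoded: number that reverses the conclusion | Removed: number that reverses it |
|---|---|---|
| 8/30 | 1 (7/30, lower limit 9.93%) | 2 (7/29 gives 10.3%; 6/28 gives 8.3%) |
| 10/30 | 3 | 4 |
| 15/30 | 8 | 10 |

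Sections 7.2 and 7.5 also mention 35 and 45 women. At n = 35 the smallest qualifying result is 8 (lower limit 10.4%), and 7/35 gives 8.4%. At n = 45 it is 10 (11.2%), and 9/45 gives 9.6%. One recoded woman again makes the difference at the margin.

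**4. Chance of meeting the 8/30 condition, for assumed k.** Suppose k of the 30 start before session 1 and are still taking AET at 1 month, and each of the others starts with probability p. The condition is met with probability P(X ≥ 8 − k), where X ~ Binomial(30 − k, p).

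| k (assumed) | p = 10% | p = 15% |
|---|---|---|
| 0 | 0.8% | 7.0% |
| 1 | 2.2% | 13.3% |
| 2 | 5.5% | 23.5% |
| 3 | 12.7% | 38.1% |

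This shows sensitivity to k. It does not predict k.

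**The case against.** Several parts of the case against this point stand, and they limit it.

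- **Starts between screening and baseline.** A reader might infer that these inflate the rate too, since baseline may come up to 14 days after consent. The documents do not support that. The AET item is asked at baseline, the rate runs from baseline, and section 4.3 places registration after the baseline assessment with a check of all eligibility criteria. A woman already taking AET at baseline is visible and is not a new initiator.
- **Length of the gap.** Nor can session 1 fall anywhere in the month. Step 2 limits the gap to about two weeks, and section 5.3 aims to schedule both sessions before the planned start.
- **A decision rule.** A reader might take the 24%/10% sentence as a go/no-go rule that one woman could overturn. It sits under the sample size justification for a preliminary estimate, and the primary endpoint is feasibility and acceptability (section 7.1). One event can move any exact binomial result across a threshold, and that alone is not evidence of bias.
- **Net upward bias.** This is not shown either. The current-use item misses women who started and stopped, and women recommended to start later may not yet be due at 1 month. Both lower the observed rate. What is certain is narrower: counting starts before session 1 can only raise a rate labelled post-intervention.
- **Re-anchoring at session 1.** A rate counted from baseline in all participants is a legitimate intention-to-treat quantity. Replacing it with a rate from session 1 is debatable. Section 2.0 accepts 70% attending at least one session, so up to 9 of 30 could attend none, and they would stay in the denominator without ever being able to count. The workbook also goes out before session 1 (Appendix 9.21), so session 1 is not a clean time zero.

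None of this answers the remaining point: the label claims an ordering that the data as described cannot show.

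**Conclusion.** The point holds as a mismatch between label and measurement in a secondary estimate. Section 7.5 counts from baseline, calls the result post-intervention, and collects nothing that separates starts in the gap of up to roughly two weeks before session 1.

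The size is unknown because the documents give no expected number of such starts, and it may be small. At the margin, one recoded woman takes 8/30 to 7/30 and 10% is no longer excluded. If such women are removed instead, it takes two. Further from the margin, several would be needed. These results rest on n = 30 and the exact 95% interval; the probabilities in step 4 rest also on assumed k and p.

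This is a cheap improvement, not an error in the primary analysis. Start dates would not make the single-arm estimate causal either. They would let the trial support the statement about timing that it already makes.

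**What to change.** 1. Add the date of first dose to the AET question at 1 and 3 months. Session dates are already recorded on the interventionist's post-session survey (Appendix 9.26).
2. In section 7.5, keep the all-participant rate, among women not taking AET at baseline, and name it initiation within one month of baseline.
3. Report separately the starts before session 1, the starts on or after session 1, and the starts among women who attended no session.
4. Use the post-intervention label, including in the sentence about excluding 10%, only for starts on or after session 1.

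**Cost.** One extra questionnaire field and a sentence or two in section 7.5. The rate called post-intervention may come out slightly lower.

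### The 37.4% ceiling on CI width in Section 7.5 holds for 30 or more evaluable women, not for up to 30; the sizes 30, 35 and 45 are unreconciled, and Section 7.6 names two analysis populations

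*Combined protocol and SAP*

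**What the plan says.** The sample size justification sits inside the Aim 2 text of Section 7.5. Its precision statement reads "With up to 30 participants, the width of the exact 95% confidence interval (CI) for the rate of AET initiation" and continues "at one month will be at most 37.4% (i.e., +/- 18.7" percentage points). A companion statement follows: "If at least 24% of participants initiate AET within one month, the study will rule out a post-intervention initiation rate of lower than 10" per cent, judged by the lower exact 95% limit.

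Three sizes appear:
- **30**, in the precision statement.
- **45**, just before it: "We may over-accrue to ensure that a total of up to 45 BCS complete the study".
- **35**, as the upper limit on sample size or accrual in Sections 1.2, 2.0, 4.1 and 7.2 and in Appendix 9.2.

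Section 7.4 marks the allowance for unevaluable participants as not applicable. Section 7.2 gives the 35 with no calculation.

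On the analysis population, Section 7.5 places Aim 2 under intention-to-treat. Section 7.6 says "The analyses for this study will focus on study completers" and, shortly afterwards, "We will use the intention-to-treat principle for analyses with all participants". Both sections mention multiple imputation ("implementing Multiple Imputation with maximum likelihood if appropriate" in 7.5, "we will use maximum likelihood with multiple imputation to account for missing data" in 7.6). Neither says which population is the denominator for the one-month initiation rate.

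**The concern.** An upper limit on n cannot give an upper limit on the width of a confidence interval, because fewer women mean a wider interval. Read literally, the statement names the most favourable case and calls it the worst. It is true only if 30 is a fixed number of evaluable women, and the protocol does not say that.

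The reader cannot repair it from the surrounding text. Forty-five completers cannot come from an accrual goal of up to 35. The 30 is not described as 35 less attrition. The two populations in Section 7.6 can give different denominators.

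This paragraph is the only quantitative support for the sample size. Section 7.2 says the pilot is to estimate effect size for a full-scale efficacy trial application, so the initiation rate and its interval are likely to be carried forward. The denominator should be fixed before the data are seen.

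**Working it through.** **Inputs.** From Section 7.5: n = 30, maximum width 37.4% (half-width 18.7%), the 24% and 10% figures, and 45 completers. From Sections 2.0, 4.1 and 7.2: up to 35 enrolled. From Section 2.0: retention above 70%, with no time point given. From Section 1.2: 10 Phase 1 interviewees.

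**Method.** The protocol says only that the interval is exact, so I assume two-sided Clopper-Pearson. For x initiators among n women:
- lower limit = 2.5% quantile of Beta(x, n − x + 1)
- upper limit = 97.5% quantile of Beta(x + 1, n − x)
- maximum width at n = the largest (upper − lower) over x = 0, …, n

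**Step 1: reproduce the plan's figure.** At n = 30 the maximum is at x = 15: width 37.41%, half-width 18.70%. This matches the protocol. Other methods at n = 30 do not (Wald 35.8%, Wilson 33.7%, mid-P 34.9%), which supports the Clopper-Pearson assumption and shows that the figure belongs to exactly n = 30.

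**Step 2: vary n.**

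| n analysed | Maximum width | Half-width | Within 37.4%? |
|---|---|---|---|
| 25 | 40.9% | 20.5 | no |
| 26 | 40.2% | 20.1 | no |
| 29 | 38.0% | 19.0 | no |
| 30 | 37.4% | 18.7 | yes |
| 35 | 34.6% | 17.3 | yes |
| 45 | 30.5% | 15.3 | yes |

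The maximum width falls at every step from n = 15 to 45. The stated ceiling is exceeded at every n from 15 to 29 and holds from 30 upward.

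**Step 3: check the 24% statement.** For each n, take the smallest count that reaches 24% and see whether its lower limit is at least 10%.

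| n | Smallest count reaching 24% | Lower limit | Rules out below 10%? |
|---|---|---|---|
| 24 | 6 (25.0%) | 9.8% | no |
| 25 | 6 (24.0%) | 9.4% | no |
| 26 | 7 (26.9%) | 11.6% | yes |
| 29 | 7 (24.1%) | 10.3% | yes |
| 30 | 8 (26.7%) | 12.3% | yes |
| 35 | 9 (25.7%) | 12.5% | yes |
| 45 | 11 (24.4%) | 12.9% | yes |

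At n = 30 the count just below, 7/30 (23.3%), has a lower limit of 9.9%, so the threshold is right there. The statement holds at every n from 26 to 45. It fails at 24 and 25, holds at 21 to 23, and fails again at 18 to 20.

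**Step 4: link the sizes.**
- All 35 in the denominator: maximum width 34.6%, and 9/35 has a lower limit of 12.5%. Both statements hold.
- Completers out of 35: the 37.4% ceiling needs at least 30 evaluable, and 30/35 = 85.7%.
- Retention only just above 70%, assumed to apply at one month: 0.70 × 35 = 24.5, so 25 completers (25/35 = 71.4%). Maximum width is 40.9%, and 6/25 has a lower limit of 9.4%. Neither statement holds.
- Thirty completers at 70% retention would need 30/0.70 = 42.9, so 43 enrolled, which exceeds 35.
- Phase 1 plus Phase 2: 10 + 35 = 45. This is a possible origin of the 45, but the protocol does not say so, and Phase 1 ran under its own protocol number.

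**The case against.** The strongest reply is that nothing has been miscalculated. The 37.4%, the 18.7 points and the 24% threshold are all correct at n = 30. The protocol regularly writes its planned size as up to some number, so the phrase may simply mean the planned 30. On that reading this part is a slip of wording. The 30 is also conservative against both other sizes, since the ceiling holds with room to spare at 35 and at 45.

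The failing case also needs several conditions together: a completer denominator, although Section 7.5 places Aim 2 under intention-to-treat; completers taken to mean women who answered at one month; a retention criterion applied at one month; and retention barely above what is a success threshold rather than an expected rate. Section 7.6 might intend a completer analysis alongside an intention-to-treat one. No decision rule in the protocol uses this interval.

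Much of this stands, and it limits the weight of the point. The figures are sound at 30, the impact is small, and the 25-of-35 case is an assumption. Three things remain. The bound as written runs the wrong way. Forty-five completers conflict with accrual of up to 35, without explanation. Section 7.6 names two populations and assigns neither to the initiation rate. However completers are defined, the ceiling needs at least 30 evaluable women.

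**Conclusion.** The point holds. The 37.4% ceiling applies only with 30 or more evaluable women. The sizes 30, 35 and 45 are not reconciled, and the denominator for the one-month rate is not fixed.

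The consequence is modest. Between 35 and 25 women analysed, the maximum half-width rises from 17.3 to 20.5 points, and the 24% statement is lost at 24 and 25. Initiation is a preliminary Aim 2 estimate, and the primary endpoint is feasibility and acceptability. The text should be corrected because it is the only numerical basis for the sample size, but the design itself is not in question.

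The conclusion rests on reading exact as Clopper-Pearson, which the match at n = 30 supports. The illustration with 25 completers further assumes that the retention criterion applies at one month and is only just exceeded.

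**What to change.** - State one Phase 2 enrolment size. Explain the 45 (for example, if it counts the 10 Phase 1 women) or remove it.
- Restate the precision for at least n evaluable women: maximum width 34.6% at 35, 37.4% at 30 and 40.9% at 25.
- Name one main denominator for the one-month initiation rate, preferably all enrolled women, in line with the intention-to-treat statements in Sections 7.5 and 7.6, and say how women without a one-month answer are counted.
- In Section 7.6, remove the completer sentence or label that analysis as a sensitivity analysis.
- Keep the 24% statement and add that it holds for 26 or more evaluable women (checked up to 45).

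The cost is protocol wording only, with no extra patients. The downside is that the stated precision becomes slightly less favourable if fewer than 30 women are evaluable.
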